12.7 Reporting of Adverse Events to IRBs/IECs

All investigators shall report AEs and SAEs, including IND safety reports, in a timely fashion to the IRB in accordance with applicable regulations and guidelines.

12.8 Reporting Pregnancy

The investigator shall be informed immediately if a female study participant becomes pregnant, or if a male participant becomes aware of a pregnancy in a female partner anytime during the year period of participation. A pregnant participant shall be instructed to stop taking study medication. The investigator shall counsel the participant and discuss the risks of continuing with the pregnancy and the possible effects on the fetus. Monitoring of the pregnant participant shall continue until the conclusion of the pregnancy.

The investigator shall report to the sponsor (DAIT/NIAID) via the SCCC all pregnancies that occur in female study participants within 24 hours of becoming aware of the event according to the procedures specified in Section 12.5.2. The Pregnancy eCRF will be used to submit the information for tracking purposes only, as the pregnancy itself is not

considered an AE or SAE. All female participant pregnancies identified during the study shall be followed to conclusion and the outcome of each must be reported. The Pregnancy information must be updated and submitted to the SCCC via the eCRF form as new information becomes available.

Information requested about the delivery shall include:

- Gestational age at delivery
- Birth weight, length, and head circumference
- Gender
- Appearance, pulse, grimace, activity, and respiration (APGAR) score at 1 minute, 5 minutes, and 24 hours after birth, if available
- Any abnormalities

All pregnancy complications that result in a congenital abnormality, birth defect, miscarriage, and medically indicated abortion should be submitted on the SAE eCRF form.

The investigator shall also report to DAIT/NIAID all male participant partner pregnancy outcomes by eCRF when this information can be obtained. Specific information collected will include number of infants; gender, weight, length, and head circumference of each infant; any infant complications, medical problems, or congenital anomalies. Informed consent will be pursued from the pregnant partner to obtain this information for the database.

12.9 Reporting Unanticipated Problems

An investigator must promptly notify the sponsor (DAIT/NIAID) via the SCCC if an “unanticipated problem involving risks to participants or others” is identified, which is not otherwise reportable as an adverse event.

12.10 Review of Safety Information

12.10.1 Medical Monitor Review

The DAIT/NIAID Medical Monitor shall receive monthly reports from the SCCC compiling new and accumulating information on AEs, SAEs, and pregnancies recorded by the study site(s) on appropriate eCRFs.

In addition, the Medical Monitor shall review and make decisions on the disposition of the SAE and pregnancy reports received from the SCCC.

12.11 Data Safety and Monitoring Board Review

12.11.1 Routine DSMB Reviews

The progress of the study will be monitored by the NIAID DSMB. The NIAID Autoimmune DSMB will be chartered to review safety data and to make recommendations to NIAID regarding continuation, termination, or modification of the study. The DSMB will review the safety data approximately 6 months after the first participant is treated.

Following the initial review, the DSMB will review the safety data twice annually during planned DSMB Data Review Meetings. Data for the planned safety reviews will include, at a minimum, a listing of all reported AEs and SAEs as well as an evaluation for a safety signal by arm by the DAIT Statistical and Coordinating Center.

The DSMB chair will be informed of any IND Safety Reports in a timely manner in order to make a recommendation for an ad hoc full board review and /or protocol suspension. Discontinuation of study treatment will also be periodically reported to the DSMB. In addition, safety data will be reviewed by the DSMB when an event occurs that

is of sufficient concern to the NIAID medical monitor or protocol co-chairs to warrant review, or when an event occurs that could contribute to a stopping rule.

12.11.2 Protocol-Defined Interim Safety Reviews

Interim safety reviews will be undertaken by a SRC comprised of a subgroup of the DSMB. The study design (Section 3.1) specifies an interim safety analysis and review by the SRC of the first dosing cohort occur one month after the last participant enrolled has completed dosing and the week 9 visit has occurred as described in Section 13.5.2. Recommendation to continue by the SRC is required, with enrollment of the second dosing cohort (every 2 months) as specified per Protocol Section 3.1.1. A second interim safety analysis and review by the SRC will take place after the last participant in the Part 1B, twelve-month dosing cohort has completed dosing and the week 48 visit has occurred.

Following the protocol-specified safety review between dosing cohorts, the SRC can recommend actions regarding study conduct, including, but not limited to, the following:

1. Continue the study as planned.
2. Add participants to an existing dosing cohort.
3. Reduce the number of weeks of study drug administration for the next higher dosing cohort.
4. Stop the study.

Recommendation by the SRC is required in order to begin enrollment in Part 2. Unless the safety data suggests otherwise the twelve-month dosing regimen will be used in Part 2.

12.11.3 Ad hoc DSMB Reviews

If any of the events listed in Safety Stopping Guidance, Section 11.5 occur, the chair of the DSMB will be notified and a review of the safety data will be performed. The DSMB will have the discretion to recommend actions regarding study conduct, and will determine if enrollment in the study should be stopped and/or administration of investigational study medication should be halted.

If any of the first 2 events occur, then no new participants will be consented, and no new participants will be enrolled, until after the DSMB completes review of the safety data. Participants in the screening phase of the study may continue to undergo minimal risk procedures.

If any of the remaining events occur, the study will proceed as planned pending DSMB review of the data. However, if two weeks has elapsed and the DSMB has not met, then no new participants will be consented, and no new participants will be enrolled, until after the DSMB completes review of the safety data.

In the event that a temporary halt is placed on consent and enrollment, participants already enrolled in the study will continue to receive study medication if they are not the participant of the DSMB review.

13 Statistical Considerations and Analytical Plan

13.1 Overview

This is a two-part multi-center clinical trial in participants with active IgG4-RD. Part 1 is an open-label phase to determine the safety and tolerability of elotuzumab and to select the duration of treatment for evaluating efficacy of the agent. Part 2 is a randomized, placebo-controlled, double-blinded phase to compare the efficacy of the addition of

elotuzumab versus placebo to prednisone in participants with IgG4-RD. The primary efficacy endpoint is disease response.

13.2 Endpoints

Primary, secondary, and exploratory endpoints are listed in Sections 3.2, 3.3, and 3.4.

13.3 Measures to Minimize Bias

In Part 2, randomization to treatment allocation will be performed to minimize bias in the comparison of the primary and secondary efficacy endpoints. Randomization will be stratified by newly-diagnosed or relapsing disease at entry to minimize confounding with the effects of treatment. In addition, the use of a placebo-controlled design for elotuzumab will minimize the risk of ascertainment bias in the IgG4-RD Responder Index and assessments of efficacy and safety endpoints in Part 2 of the study.

13.4 Analysis Plan

13.4.1 Analysis Populations

In Part 1:

Safety population: will be defined for each treatment regimen as all participants who received any amount of investigational product.

In Part 2:

Modified Intent-to-Treat (mITT) population: will be defined as all participants who undergo random assignment and receive any amount of elotuzumab / elotuzumab-placebo. The primary efficacy analyses will be based on the mITT population according to the groups to which the participants are assigned.

Per Protocol (PP) population: will be defined as the subgroup of participants in the mITT population who (1) receive at least 5 of 6 elotuzumab / elotuzumab-placebo infusions or discontinue treatment due to a disease flare (2) receive at least 80% and no more than 120% of the cumulative dose of prednisone during the 10 week taper defined in Section 7.1.1.3, (3) adhere to the permitted single course of glucocorticoids for non-IgG4-RD indications defined in Section 7.2 and (4) have no major protocol deviations or ineligible entry criteria that would impact efficacy assessments through week 48.

A masked data review will evaluate deviations from the protocol in a blinded manner for impact on the efficacy assessments and exclusion from the PP population. This may include, but is not limited to, violations of entry criteria, departures from assigned treatment regimen, modifications of concurrent therapy, failure to complete study visits, or administration of study procedures outside the specified visit windows.

Safety population: will be defined as all participants who received any amount of at least one elotuzumab / elotuzumab-placebo infusion. Safety analyses will be based on the actual treatment which the participants receive.

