3.6.4 Safety

The following safety parameters will be recorded at regular intervals during the study:

- All adverse events using the grading criteria described in Section 12.3.1
- Clinical laboratory testing (clinical chemistry, hematology, and urinalysis)
- Concomitant medications: Any medication related to IgG4-RD taken at any point should be recorded. Other non-IgG4-RD related concomitant medications taken 30 days prior to screening through study completion or termination should be reported.

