4.2 Exclusion Criteria

Individuals who meet any of these criteria are not eligible for enrollment as study participants:

1. Presence of a condition other than IgG4-RD that (e.g., asthma) is likely to require systemic Glucocorticoids (GC) for disease control during the period of the trial.

¹ Vaccination status must conform to CDC recommendations for immunocompromised individuals. These recommendations are subject to change, but are updated at: <https://www.cdc.gov/coronavirus/2019-ncov/vaccines/recommendations/immuno.html>.

2. Malignancy within 5 years (except successfully treated in situ cervical cancer, resected squamous cell or basal cell carcinoma of the skin.)
3. The following lab values as indicators of hepatic dysfunction:
 - a. Serum aspartate aminotransferase (AST) or alanine aminotransferase (ALT) greater than three times the upper limit of normal (ULN)
 - b. Total bilirubin > two times the ULN unless caused by Gilbert's disease. Gilbert's disease with total bilirubin > three times ULN.
 - c. Serum albumin < 2.5 gm/dL.
4. Evidence of another uncontrolled condition which, in the judgment of the investigator, could interfere with participation in the trial according to the protocol.
5. Active infection requiring hospitalization or treatment with systemic antimicrobial agents within the 30 days prior to treatment allocation/randomization.
6. Prior use of rituximab or other B cell depleting agents within 9 months of enrollment unless B cells have been demonstrated to have repopulated.
7. Use of any investigational agent or biologic and non-biologic DMARDs within 5 half-lives of the agent (or 6 months if the half-life is unknown) prior to enrollment.
8. Any of the following laboratory tests at the Screening Visit:
 - a. White blood cell count (WBC) < 3.0 x 10³/µL.
 - b. Absolute neutrophil count (ANC) < 1.5 x 10³/µL.
 - c. Hemoglobin < 10 g/dL.
 - d. Platelet count < 75 x 10⁹/L.
 - e. Estimated glomerular filtration rate (eGFR) ≤ 45 ml/minute/1.73 m².
9. The use of supplemental oxygen at baseline.

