7.2 Standard of Care Recommended/Permitted Therapies

- Course of glucocorticoids for non-IgG4-RD indications that are discontinued within 2 weeks: only 2 such courses are permitted and must be complete by 8 weeks prior to the Week 48 visit.
- Potential participants are encouraged to obtain vaccines as standard of care per age-specific Center for Disease Control and Prevention (CDC) guidelines before participating in the study. Live vaccines must be avoided within 8 weeks of initiation of study drug. If possible it is suggested participants obtain other immunizations at least 4 weeks prior to initiation of study therapy. Seasonal flu vaccine should be obtained during the course of the study. Other non-live vaccines as needed for standard of care may be administered.
- Concomitant therapies taken for the long term treatment of pre-existing conditions other than IgG4-RD may be continued during the study provided they are in accordance with the exclusion criteria and the list of prohibited medications. During the study, concomitant medications and new medications should be administered at the discretion of the site investigator or treating physician in order to provide the participant with the best possible medical care.
- Medications used for prevention and treatment of COVID-19, approved by the FDA or authorized for emergency use, are permitted.
- Participants should continue to receive SARS-CoV-2 vaccinations per CDC and FDA recommendations and other seasonal vaccinations during the course of the study.

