13.4.2 Primary Analysis of Primary Endpoint

Part 1

Descriptive statistics will be used to summarize the proportion of participants in each cohort who experience at least one Grade 3 or greater adverse event during study participation for all participants in the safety population. The primary analysis of efficacy and safety endpoints will be conducted after all participants in Cohort 1a and 1b complete the Week 48 assessments or are withdrawn from the study.

Part 2

The primary endpoint for Part 2 is disease response at 48 weeks, defined as the percent improvement in the IgG4-RD RI score over baseline:

$$\% \text{ Improvement in IgG4RD RI}_{\text{Week 48}} = 100 * \left(\frac{\text{IgG4RDRI}_{\text{Baseline}} - \text{IgG4RDRI}_{\text{Week 48}}}{\text{IgG4RDRI}_{\text{Baseline}}} \right)$$

For participants whose IgG4-RD RI score is worse (e.g. higher) at week 48 than baseline, their % Improvement in IgG4-RD RI_{Week 48} will be considered 0%. Additionally, participants who use glucocorticoids or other immunosuppressants beyond that permitted by protocol, or who experience a disease flare as defined in Section 3.5.3 at any time point before 48 weeks will be defined as achieving no disease response (0%).

The observed levels of disease response at 48 weeks will be summarized by arm in the mITT population as the median, interquartile range, and range. A between-group comparison of the assessment of disease response at 48 weeks will be performed using a Wilcoxon-Mann-Whitney test with a two-sided Type I α of 0.05, and will be reported with a two-sided 95% confidence interval for the Mann-Whitney parameter (Section 13.6) derived under the proportional odds assumption [41]. The primary analysis of disease response will treat all participants who drop out of the study prior to reaching week 48 for any reason, including a disease flare, initiation of non-protocol therapy, or any other reason to cause them to be unevaluable using the IgG4 Responder Index, as having no disease response (0% improvement) for the primary endpoint. The primary analysis will be conducted after all participants in Cohort 2 complete the Week 48 assessments or are withdrawn from the study.

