13.4.3 Supportive Analyses of the Primary Endpoint

A supportive analysis of the primary endpoint will consider participants who drop out of the study prior to reaching week 48 without evidence of disease flare, initiation of non-protocol therapy, or other indications of increased disease activity as missing-completely-at-random (MCAR). Descriptive statistics and the Wilcoxon-Mann-Whitney test will be repeated in the subgroup of the mITT population excluding participants with data MCAR. A masked data review panel will evaluate participant disposition and all disease activity assessments in a blinded manner to define the types of missing data. In addition, analysis of the primary endpoint will be repeated as a van Elteren test with a covariate for the stratification factor of newly-diagnosed versus relapsing disease at study entry. As an additional supportive analysis which does not assume data are MCAR, a two-dimensional tipping point analysis of missing data will be conducted. Additional details on supportive analysis will be specified in the Statistical Analysis Plan.

Supportive analyses of the primary endpoint will be repeated in the PP populations and as a preplanned subgroup analysis in participants who are identified as having elevated serum IgG4 level prior to initiation of study therapy. The subgroup is defined as any serum IgG4 concentration greater than 1.5 times the upper limit of normal that is obtained within 6 months of the Baseline visit or at the baseline assessment of Serum IgG subclasses.

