13.4.4 Analyses of Secondary and Other Endpoints

The key secondary endpoint for Part 2 is complete response at 48 weeks, defined as an IgG4-RD RI Score of 0 and a glucocorticoid dose of 0 mg/day and no flare since beginning treatment. A fixed sequence testing procedure will be conducted with the primary efficacy endpoint, to control the overall Type I error rate at 0.05. Specifically, if the between-group comparison of disease response at 48 weeks reaches statistical significance, a comparison of the rates of complete remission at 48 weeks will be performed using a Fisher's Exact test with a two-sided Type I α of 0.05. If the between-group comparison of disease response at 48 weeks fails to reach statistical significance,

inferences on complete remission will be supportive without overall Type I error control. The proportion in complete remission in each arm will be reported with two-sided 95% Clopper-Pearson confidence intervals. All participants in the mITT population who drop out of the study prior to reaching week 48 for any reason, including a disease flare, initiation of non-protocol therapy, or any other reason to cause them to be unevaluable using the IgG4 Responder Index, will be defined as not achieving complete remission.

All inferential analyses for the additional secondary efficacy endpoints are considered supportive; p-values for test of differences among groups will be presented without adjustment for multiple comparisons. All secondary endpoints will be analyzed in the mITT and PP populations, and in the subgroup with elevated serum IgG4 level prior to initiation of study therapy.

For all dichotomous efficacy endpoints, Fisher's Exact tests will be conducted and two-sided 95% Clopper-Pearson confidence intervals will be reported.

Frequency counts of the number of disease flares and the number of organ sites with disease-related damage will be reported by arm, and between-group comparison will be performed using Fisher's Exact Test.

For secondary continuous efficacy endpoints, including the Physician Global Assessment and Patient Global Assessment, descriptive statistics will be used to summarize the distribution of scores in each arm. The absolute change from baseline will be analyzed using an analysis of covariance model (ANCOVA) with treatment allocation as the independent variable.

Treatment group differences for the safety endpoints will be compared using a Fisher's exact test.

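### Per-protocol criterion (3) allows one non-IgG4-RD glucocorticoid course and cites Section 7.2, but Section 7.2 allows two

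*Combined protocol and SAP*

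**What the plan says.** Section 13.4.1 defines the Part 2 PP population by four criteria. The third is that participants "adhere to the permitted single course of glucocorticoids for non-IgG4-RD indications defined in Section 7.2".

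Section 7.2 describes the permitted use as "Course of glucocorticoids for non-IgG4-RD indications that are discontinued within 2 weeks" and then sets the limit: "only 2 such courses are permitted and must be complete by 8 weeks prior to the Week 48 visit". Section 7.3 exempts glucocorticoids covered by Section 7.2 from the list of prohibited medications.

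Two groups of analyses use the PP population. Under Section 13.4.3, "Supportive analyses of the primary endpoint will be repeated in the PP populations". Under Section 13.4.4, "All secondary endpoints will be analyzed in the mITT and PP populations".

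The primary analysis in Section 13.4.2 uses the mITT population. It assigns 0% improvement to "participants who use glucocorticoids or other immunosuppressants beyond that permitted by protocol", so its limit is whatever the protocol permits elsewhere.

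**The concern.** Criterion (3) presents itself as a restatement of Section 7.2 but gives a different number. A participant with exactly two short courses that meet Section 7.2 is in an undefined position. On the literal wording that participant fails criterion (3) and leaves the PP population. If the cross-reference governs, the participant stays.

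The primary endpoint rule depends on the same permission and does not share the ambiguity, because Section 7.2 is where the protocol sets the permitted number. On the literal reading, one treatment history is acceptable for the primary analysis and disqualifying when the supportive analyses are repeated in the PP population. A difference between the mITT and PP results is meant to show the effect of departures from the protocol. Here it would also reflect the removal of people who kept to this part of it.

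If the number is not settled in advance, someone must choose it when the PP population is assembled.

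**Working it through.** **1. The sections side by side**

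| Section | Role | Courses allowed |
|---|---|---|
| 7.2 | Sets the permission | 2, each stopped within 2 weeks, complete by 8 weeks before Week 48 |
| 7.3 | Prohibited medications | Defers to 7.2 |
| 13.4.2 | 0% rule for the primary endpoint | Whatever the protocol permits, hence 7.2 |
| 13.4.1, criterion (3) | PP membership | 1, attributed to 7.2 |

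No other section limits participants to one course. The mismatch is in current text, not in a record of superseded wording.

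**2. How many participants could be affected**

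The documents give no rate of non-IgG4-RD glucocorticoid courses, so the rate is assumed. Let the number of courses per participant over 48 weeks be Poisson with mean m. Then P(exactly two) = exp(−m) × m²/2.

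Only courses complete by Week 40 (48 − 8) comply with Section 7.2. If completion times are uniform over 48 weeks, both are in time with probability (40/48)² = 0.694.

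| m (assumed) | P(exactly two) | × 63 | × 63 × 0.694 |
|---|---|---|---|
| 0.1 | 0.0045 | 0.29 | 0.20 |
| 0.25 | 0.0243 | 1.53 | 1.06 |
| 0.5 | 0.0758 | 4.78 | 3.32 |

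Two things pull these counts down. Some of these participants would fail another PP criterion anyway. Exclusion Criterion 1 (Section 4.2) also removes anyone with another condition that "is likely to require systemic Glucocorticoids (GC) for disease control during the period of the trial". A likely range of 0 to 2 of 63 is a judgement from these two points, not a calculation.

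**3. Scale of the loss, as illustration only**

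The plan's own figure comes first. Noether's formula with allocation c = 2/3, δ = 0.75, two-sided α = 0.05 and 90% power gives

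N = (z₀.₉₇₅ + z₀.₉₀)² / [12 × c(1 − c) × (δ − 0.5)²] = 63.04,

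which matches the 63 in Section 13.7.

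The corresponding power is Φ(√[N × 12 × (2/3)(1/3) × 0.25²] − 1.96):

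- N = 63: 0.900
- N = 62: 0.895
- N = 61: 0.890

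This holds allocation at 2:1 and supposes that nobody leaves the PP population for any other reason. The PP analyses are not powered, so the figures show only that losing one or two participants changes little.

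**The case against.** The strongest reply is that little depends on this. The primary analysis is mITT, and the key secondary endpoint has its own place in the fixed testing sequence. The other secondary inferences are declared supportive, so no confirmatory conclusion turns on PP membership. That is correct, and it limits the weight of the point.

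A second reply is that a PP population need not contain everyone who complied. Criterion (1) requires at least five of six infusions, yet a participant can fall below five because the protocol itself required doses to be withheld or treatment to be stopped. A stricter glucocorticoid limit could therefore be a legitimate choice. This stands as a general matter, but criterion (3) does not present itself as stricter. It describes the single course as what Section 7.2 permits, and that is not so.

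A third reply is that the cross-reference lets Section 7.2 govern, or that the masked data review will resolve such cases. The first part is a fair reading, but it concedes that the word for one course is wrong. As for the second, the review covers modifications of concurrent therapy and could bring these participants to light before unblinding. Its stated task, however, is to judge deviations. Two compliant courses are not a deviation, and the review is given no rule for choosing between the two limits.

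Finally, Section 13.4.3 leaves further detail on supportive analyses to a Statistical Analysis Plan. The text available does not show whether that plan corrects the PP definition.

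**Conclusion.** The concern holds. Criterion (3) in Section 13.4.1 is an internal inconsistency in an operative rule: it cites Section 7.2 for one course where Section 7.2 permits two. Taken literally, it excludes participants with two compliant courses from all PP analyses of the primary and secondary endpoints.

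The size is small. Two compliant courses would be expected in about 0.2 to 3.3 of 63 participants under the assumed Poisson means of 0.1 to 0.5 and uniform completion times, and 0 to 2 is the more likely range. Those counts rest on assumptions; the textual conflict does not. It should be corrected because the error is definite and the correction is nearly free.

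**What to change.** Reword criterion (3) along these lines: *adhere to the limits on glucocorticoid courses for non-IgG4-RD indications permitted in Section 7.2*. The number then appears in one place only, and the primary endpoint is untouched.

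If one course is what is clinically intended, amend Section 7.2 instead. That is the larger change, because it would also alter who is scored 0% under Section 13.4.2. If the PP population is meant to be deliberately stricter than the protocol, say so and remove the attribution to Section 7.2.

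Whichever is chosen, settle it before unblinding so that the choice cannot be influenced by results.

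The cost of the recommended change is one phrase in Section 13.4.1. The sample size and visits do not change. The data are already collected, since Section 3.6.4 states "Other non-IgG4-RD related concomitant medications taken 30 days prior to screening through study completion or termination should be reported".

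Optionally, and separate from the error, a sentence in Section 7.2 could confirm that glucocorticoids given as premedication or for an acute infusion reaction are permitted and do not count as a course.
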